#### ***Box 1. T-Wellness Components***

- One-day Workshop (covered 5 topics)
  - Understanding stress and job burden
  - Managing stressors
  - Explaining mood
  - Cognitive and behavioral strategies for managing mood
  - Teacher-to-teacher support and other supports
- Three monthly teacher group-support sessions (1 hr each)
- Referral for severe distress teachers

[figure not shown]
Two Advisory Boards (N=10; 1 rural and 1 urban advisory board) will be established to ensure that the *PD* effectiveness-implementation study aligns with Ugandan school/health system policies and practices in communities to pave the way for a sustainability policy plan should the intervention be effective. The Board in the urban setting will include 6 representatives, including 2 Ministry stakeholders, 1 researcher, 1 NGO stakeholder, 1 teacher, and 1 parent leader. The Board in the rural setting will include 4 representatives, including 1 local-MOE leader, 1 researcher, 1 teacher, and 1 parent leader. The teacher and parent leader will be selected based on school stakeholders' recommendation. The advisory boards will meet regularly (2 times a year) throughout the 4 study years and provide guidance on programming, finding interpretation, and dissemination. Meeting notes will be documented for analyses.

In Years 2-4, we will carry out a cluster randomized controlled trial to study effectiveness and mechanisms of intervention with 36 schools. Implementation and evaluation activities will be carried out in two-cohort sequence by recruiting school staff and families (children and their caregivers).

- *Primary school teachers and selected school leadership staff* (Head teacher, PTA leaders) will participate in the evaluation study for 2 years. Teachers (i.e., pre-primary and primary 1st to 4th grade, serving students between the ages of 3 and 10 years) and PTA leaders are the primary targets of the PD/PDT.
- *Children and caregivers* will participate in the Year 2-4 RCT evaluation study for 18 months which will include surveys/Questionnaires/Individual Interviews for the caregivers and game-like activities for children that assess childrens' attention, memory, and social emotional wellbeing.

#### 4.6 Total Number of Participants and Sites

This study is carried out in Uganda with support from the US. Recruitment, informed consent, intervention, and evaluation of all school staff and participating families will occur in Uganda. For the PD/PDT effectiveness evaluation, participants will include 540 school staff (i.e., teachers/principals from 36 schools), 24 PTA members from intervention schools, and 8 implementers (from TTCS and mental health institutions). There will be 1980 parent-child pairs (including 1980 parents/caregivers and 1980 children). We expect that most teachers and primary caregivers/ parents will be female (75%), and equal % for children will be male and female (50% for each group). Participants numbers break down by site (rural and urban) are presented in the figure below.

## **4.7 Participant Withdrawal or Termination**

### **4.7.1 Reasons for Withdrawal or Termination**

Participant will be free to withdraw from participation in the study. Participants can request to discontinue participation at any time. The decision to participate or not participate, or to withdraw, will not affect participant employment and/education opportunity

### **4.7.2 Handling of Participant Withdrawals or Termination**

To leave the study, Ugandan participants will be asked to send a written notice to [name] and [name]. at the following address: (Department of Psychiatry, Makerere University, Kampala, Uganda), or email Drs. [name] and [name].

### **4.7.3 Premature Termination or Suspension of Study**

This study may be temporarily suspended or prematurely terminated if there is sufficient reasonable cause. If the study is prematurely terminated or suspended, the PIs will promptly inform the IRB and will provide the reason(s) for the termination or suspension.

Circumstances that may warrant termination or suspension include, but are not limited to:

- Determination of unexpected, significant, or unacceptable risk to participants
- Insufficient compliance with protocol requirements
- Data that are not sufficiently complete and/or evaluable
- Determination of futility

## **5 Behavioral/Social Intervention**

The EBI considered in this study is ParentCorps-Professional Development (PD), a school-based EBI and preventive service provision model that supports teachers and school personnel to apply EBI strategies to promote young children's mental health in impoverished areas. The PD approach represents a task-shifting model of mental healthcare by shifting mental health preventive duties from professionals to teachers to optimize school children's mental health. Therefore, teachers are considered as CHWs. Two efficacy studies of PD from our work in urban Uganda (RCT in 10 schools; 1R21MH-097115-01A1) and rural Nepal (pre-post comparison in 30 schools; UBS Foundation) demonstrate feasibility, acceptability, and positive impacts on teachers' use of EBI strategies and students' mental health. The current study builds on this work and further tests scalable PD implementation approaches and investigates PD effectiveness in multiple regions (urban and rural) in Uganda. In addition, based on previous findings that nearly 80% of Ugandan teachers (the EBI strategy users) experience occupational stress that threatens PD uptake, effectiveness, and sustainment, this study will also test a teacher stress management package (T-Wellness, adapted from EBIs) as an enhancement to PD.

The 24 schools assigned to the intervention conditions will receive PD (12 with and 12 without T-Wellness) during their 1st year of participation. In the PD group, teachers and PTAs will participate in a 3-day ParentCorps-PD training before the 1st school term. For the PDT group, one additional training day will be added for stress management. Teachers in both PD implementation conditions will also receive 8 sessions (12 hours) of face-to-face group-based coaching during the 1st and 2nd terms. Coaching sessions are to help teachers apply EBI strategies in their classrooms, engage families, and develop competencies. For the teachers in the PDT group, additional stress management group coaching activities will also be integrated into the 8 sessions (3 additional monthly 1-hr wellness sessions for teachers as a group in each school) and receive a total 15 hours of coaching.

## 6 Study Procedures and Schedule

### 6.1 Study Procedures/Evaluations/Procedures/Timeline

The three effectiveness and mechanism testing aims (Aim 1-3) will be accomplished by applying a matched-pair cRCT and hybrid effectiveness-implementation design. A mixed methods design with qualitative and quantitative data collection will be applied. The school will be the unit of randomization because the program is applied at the school-level and builds a “school community” of teachers who promote students’ mental health. The three-arm cRCT design allows us to simultaneously test *PD* effectiveness and study the added value of a package (T-Wellness) to address a critical practical task-shifting challenge (teacher stress). In addition, the Hybrid design that considers CFIR domains of implementation contexts (in Figure 1) allows us to rigorously study other EBI effectiveness-implementation mechanisms, which can further inform decisions about optimal deployment and generalized impact, and may accelerate the introduction of other valuable innovations into practice. Study tasks and timeline are listed in Table 1 below.

For effectiveness, intervention theory of change (mediation mechanisms), and cost-benefit evaluations, the child and teacher effectiveness outcomes will be assessed and evaluated across 3 time points- baseline (**T1**, before PD), immediately after the PD/PTD (**T2**, about 3-4 months after T1), and 12 months later (**T3**, about 18 months after T1). Data from **multiple sources** will be collected. For child effectiveness outcomes, the primary outcome is mental health (externalizing and internalizing problems), and the secondary outcome is behavioral and cognitive domains (see Table 2 for measures). Parent and child report data will be used. Parents of target students will be interviewed by trained research staff (using English or Luganda, lasting 30-45 minutes). Child assessment will be carried out in school by research staff (lasting about 20-30 mins). For teacher effectiveness outcomes, the primary teacher outcome is EBI practice, which will be based on objective observation by an independent observation team (primary data source) and teacher-report (secondary data source). The observation measure has been validated and published in our previous trial study (see [name] KY, [name] J, et al. Transportability of an Evidence-based Early Childhood Intervention in a Low-Income African Country: Results of a Cluster Randomized Controlled Implementation Study. *Prevention Science*. 2017;18:964-75). The secondary teacher outcome will be social process (i.e., teacher-student and teacher-family relationship), based on parent and child report. All primary outcomes and most secondary outcome measures have been used and validated in our previous Ugandan studies (see Table 2 for measures and reliability information from our Ugandan studies). Costs will be measured using an activity-based micro-costing approach in the intervention cluster (school), and in the extended implementation phase in all clusters from 6 through 12 months (n=36 clusters). Costs of the intervention will include all program costs incurred (for *PD/PDT* training, coaching, and materials/resources). Research costs will be excluded. Cost data collection will utilize existing standardized cost extraction forms and procedures that have been validated from Co-I [name]’s work in Uganda and LMICs. Prior to use, these tools will be tailored and customized. **Research staff for family and observation data collection will be masked** to intervention conditions. To ensure masking, we will have an independent assessment team (led by a separate research coordinator), and members will not participate in any intervention activities. We will also train implementation team on protocol to prevent releasing assigned condition information. Teacher-report data collection will not be masked. The tablet and team approach of data collection that we used in our previous studies will be applied.

For study implementation moderation mechanisms, the selected key moderators from the 5 CFIR domains include target individuals’ characteristics (teachers and children), school, and intervention implementation contexts will be studied (listed in Table 2). Most CFIR measures have been validated in our previous *PD* pilot trial. *PD/PDT* implementation fidelity will be assessed, characterized, and examined for moderation effects (on teacher effectiveness outcomes). Four fidelity measures will be considered, including *adherence* (the extent to which the TTC trainers deliver the core intervention content and as per program guidelines), *quality of program implementation* (assessed based on teacher satisfaction with the *PD/PDT* and ratings of TTC Coaches’ competence); *engagement* (assess trainees’ level of *PD* knowledge improvement from pre- to post-training); and *exposure* (measured by attendance of *PD* and coaching sessions).

To have a more comprehensive understanding of possible mechanisms, we also plan to conduct qualitative interviews, which will purposively select *PD* trainers (n=8), teachers (n=40; 20 from intervention and 20 from control across two sites) and our Advisory Board members, and conduct interviews at 4 time points (T1, T2, T3,

and Year 4). Interview guides will comprise semi-structured questions relating to experience with *PD/PDT*. Participants will also be asked to provide a narrative account of partnership approaches, efforts to implement *PD/PDT*, including barriers and facilitators experienced. The group interview guides will be adapted from our previous pilot *PD* implementation studies.

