Phase	Phase II/III
Objectives	This study include three specific aims: Aim 1. To evaluate the short- and longer-term effectiveness of, PD alone ( PD ), PD + T-Wellness ( PDT ), and control (C, provision of child mental health and referral information). Hypotheses: (a) PD is more effective than control; and (b) PD with T-Wellness ( PDT ) is more effective for CHWs/teachers than PD alone; and (c) PDT has a more favorable cost-effectiveness ratio than PD alone; Aim 2. To examine effectiveness mechanisms and theory of change underlying the EBIs. Hypotheses: the mediational mechanisms of PD (teacher EBI strategy use as a mediator between intervention and child outcomes) and PDT (teacher stress management and EBI strategy use as mediators) will be supported; Aim 3. To examine implementation contextual factors and mechanisms that contribute to CHWs' (teachers') uptake and sustainment of EBI strategies within PD and PDT schools. Hypotheses: better fidelity, teacher mental health and more supportive contexts will be associated with better teacher uptake and sustainment of EBI strategies and more effective task-shifting.

Methodology	A cluster randomized controlled trial (cRCT), single blind and mixed-methods design will be applied. All study activities will be conducted in Uganda. Thirty-six public primary schools (18 urban and 18 rural), 540 teachers (~15 per school) and 1,980 parent-child pairs (~55 per school) will be recruited. Schools will be assigned to one of three conditions (PD, PDT, control). A stratified-block randomization procedure will be applied to ensure approximately similar characteristics across study regions and conditions.
Endpoint	Effectiveness outcomes will be assess 3 times (Time 1= before intervention; Time 2= immediate after PD/PDT intervention; Time 3= 12 months after Time 2). The primary teacher effectiveness outcomes (or intermediate effectiveness outcomes) are teachers' EBI strategy use and teacher stress management. The primary child effectiveness outcomes are child externalizing and internalizing problems (mental health outcomes). The secondary child effectiveness outcomes are emotion regulation, executive functioning (ability for cognitive processes that are foundation for the cognitive control of behavior), and social relationship (student-teacher relationship, peer relationship).

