Population	The study populations include: (1) Teachers for the T-Wellness User-centered & Optimization testing (n=60; from 4 non-RCT schools in year 1); (2) Intervention implementers (n=8; 6 TTC trainers and 2 mental health professionals from urban/Kampala and rural/Hoima regions; (3) Primary school teachers/head teachers (n=540) from 36 schools and PTA leaders (n=24) from 24 intervention schools; and (4) Children and caregivers (n= 1980 parent-child pairs) from 36 study schools.
Study Sites	36 schools (12 receiving PD, 12 receive PDT, and 12 control).
Number of participants	2544 adults and 1980 children for Aims 1-3 (This is not including 60 teachers for the T-Wellness User-centered testing during Year 1 preparation year).

[figure not shown]

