##### **Recruitment and Referral Sources:**

- Intervention Implementer/ Trainer: Drs. [name] and [name] We will work with TTC and, MOE, and MOH to finalize the referral and recruitment process. Trainers will be identified and invited to participate. Participation will be completely voluntary, with no consequence for opting out of participation due to personal reasons.
- Schools: We will work with Ministry of Education (MOE) to finalize the referral and recruitment procedure. In general, public primary schools in targeted districts will be identified from governmental school lists in two study districts (urban and rural) provided by MOE. Principals of these schools will be invited to attend one of the information sessions hosted by the Ugandan intervention implementation team. During the recruitment session, principals will be provided with details of study requirements and intervention. They will have an opportunity to ask questions and also complete a questionnaire that seeks to gather information on school demographics, commitment to remain in a randomized condition, willingness to facilitate data collection, and allocate staff time to participate in the study. Eligible schools will be selected based on school leaders' and principals' expressed of interest and their agreement to allow teachers' voluntary participation. To ensure approximately similar characteristics in the intervention and control conditions, a statistician, unfamiliar with study schools, will match schools on size (i.e., number of teachers and students), location (urban/rural), and quality/performance from the eligible school list. A stratified-block randomization design will be applied. We will work with MOE to finalize a systematic approach to select the final 36 schools.

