## 9 Statistical Considerations

**Data Analysis Plan for Aim 1.** Prior to any outcome analyses, we will generate summary statistics for all data, summarizing with means and standard deviations for continuous variables and frequencies for categorical variables. The distribution of study variables and missing data patterns will be inspected. To estimate effectiveness, we will apply intention-to-treat (ITT) analyses and first focus on between-subject comparisons of intervention vs. control (comparing *PD* to control, comparing *PDT* to control, and comparing *PD* to *PDT*). We will estimate the impact of *PD* on children and teachers post-intervention (T2, 4-5 months after T1) and at one-year follow up (T3, 18 months after T1, or 12 months after T2). **Figure 4** below describe the model to be tested under Aim 1. School and class nesting will be considered, and a multiple imputation strategy will be applied to account for missing data. Linear mixed effect models, using SAS PROC MIXED, will be applied to examine short and longer-term impacts. We will first examine the immediate impact by modeling post-intervention outcomes (T2) as a function of intervention, adjusting for T1 outcome measures. The model accounts for between-subject (within-school and -class) correlation by including school- and classroom-level (when appropriate) random intercepts. The outcomes will be modeled as:  $Y_{ij} = \beta_1 I_j + \beta_2 C + \beta_3 X_{ij} + \gamma_j + \gamma_k + \epsilon_{ijk}$ , where  $Y_{ij}$  is the outcome for the student  $i$  in school  $j$ .  $I_j$  is intervention status (a categorical variable, with 3 levels) for school  $j$ , representing two dummy variables (control as the reference).  $C$  is the cohort indicator for

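### The plan calls a three-arm trial matched-pair, does not say what constrained allocation, and leaves matching out of the Aim 1 models, so standard errors may be too wide.

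*Combined protocol and SAP*

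**What the plan says.** Section 6.1 states that the three aims "will be accomplished by applying a matched-pair cRCT and hybrid effectiveness-implementation design". The same paragraph then says "The three-arm cRCT design allows us to simultaneously test" PD effectiveness and the added value of T-Wellness. The Protocol Summary gives the allocation as "36 schools (12 receiving PD, 12 receive PDT, and 12 control".

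In section 4.4 (Recruitment and Referral Sources, Schools), a statistician unfamiliar with the schools "will match schools on size (i.e., number of teachers and students), location (urban/rural), and quality/performance from the eligible school list". The next sentence reads "A stratified-block randomization design will be applied". Strata and blocks are not defined there or elsewhere, and the text does not say whether the matched sets serve as blocks.

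Section 9 gives two Aim 1 models. The T2 model has arm, cohort and the T1 value of the outcome. On clustering it says: "The model accounts for between-subject (within-school and -class) correlation by including school- and classroom-level (when appropriate) random intercepts". The longer-term model adds time, arm-by-time and, in the text, school-level random slopes. Neither model has a term for matched set, randomisation stratum, school size, school performance or region. Region enters the plan only as the primary moderator (Table 2 of section 6.1).

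**The concern.** There are two linked problems.

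First, the design label cannot describe this allocation. Matched pairs do not divide among three arms in equal numbers, so an analyst reading the plan cannot reconstruct how schools were randomised.

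Second, matching on size and performance is meant to take school-to-school differences out of the arm contrasts. If matched sets or strata constrain who can be allocated where, the true variance of a contrast falls. A model that omits them goes on estimating the larger, unrestricted variance. Intervals are then wider than they need be and the test runs below its nominal level. Only 12 schools per arm carry each of the three pairwise contrasts, so lost precision would matter.

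**Working it through.** **No planned figure to reproduce.** The documents contain no power calculation, ICC, alpha or matching correlation. The counts are consistent: 36 × 55 = 1,980 and 36 × 15 = 540, as in "Thirty-six public primary schools (18 urban and 18 rural), 540 teachers (~15 per school) and 1,980 parent-child pairs (~55 per school) will be recruited".

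**Inputs from the documents.** 12 schools per arm; about 55 children per school; d = 0.2, the low end of the 0.2–0.4 range in section 9. That range is a cost-effectiveness benchmark, not a design target.

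**Assumptions.** Outcome SD 1 and ICC 0.05, both taken as what remains after baseline adjustment; two-sided 5%; no dropout; twelve sets of three schools, one per arm. Let r be the share of between-school variance that lies between sets.

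**Variance of a school mean.** v = ICC + (1 − ICC)/55 = 0.05 + 0.95/55 = 0.0673.

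**SE of one contrast.**
- Estimated without a set term: √(2v/12) = √(2 × 0.0673/12) = 0.106, whatever r is.
- True value under set-wise allocation: √(2(v − 0.05r)/12). At r = 0.3 this is √(2 × 0.0523/12) = 0.093, so the estimated SE is about 13% too large. At r = 0.5 it is √(2 × 0.0423/12) = 0.084, and the excess is about 26%.

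**Power.** With a set term, the contrast follows a noncentral t on 22 df with noncentrality 0.2/(true SE): 1.889, 1.963, 2.143 and 2.383 for the four rows below. Without it, the test uses arm only on 33 df. Its power and size come from simulated school means (400,000 trials per setting).

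| r | True size, no set term | Power, no set term | Power, set term |
|---|---|---|---|
| 0 | 5.0% | 44.8% | 43.9% |
| 0.1 | 4.2% | 45.0% | 46.7% |
| 0.3 | 2.8% | 44.2% | 53.5% |
| 0.5 (upper case) | 1.6% | 44.1% | 62.5% |

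At r = 0.05 the two analyses have nearly equal power. At d = 0.3 the pattern is the same with smaller gaps: 81.4% and 86.7% at r = 0.3. At ICC 0.10 and d = 0.2, r = 0.3 gives 25.9% and 35.7%.

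**Cost of a useless set term.** The df fall from 33 to 22 and the critical value rises from 2.035 to 2.074, or about 1 point of power.

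**Could the allocation have been made without triplets?** Yes. With 18 urban and 18 rural schools and two cohorts of 18 (data-collection rows of Table 1, section 6.1), an even region-by-cohort split would give four strata of 9 schools, 3 per arm. That also totals 12/12/12.

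**The case against.** The strongest reply is that matched sets are inferred. Apart from the one label in section 6.1, the randomisation method given in the Protocol Summary and section 4.4 is stratified-block. The matching sentence sits in the paragraph on choosing the final 36 schools, so it may describe picking comparable schools or defining strata. A reader might infer from 12/12/12 that twelve triplets were randomised. The documents do not support that, because region-by-cohort strata give the same totals. This part of the reply stands, and any instruction to fit a triplet term must be conditional.

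The reply also says that the loss is not automatic, which is correct. Baseline adjustment already absorbs part of the between-school variance. If sets lie within cohort, the planned cohort term absorbs part of the set variance too, and the arm-only comparator above has no such term. Nothing in the documents shows that school size or performance predicts parent-reported child problems once the T1 score is in the model. The r = 0.5 row is therefore an upper case.

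A reader might also infer a risk of false positives. There is none from this source: leaving out a set or stratum term that constrained allocation biases no estimate and makes the test conservative.

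The reply does not remove the label that contradicts the number of arms, the undefined blocks, or the absence from Aim 1 of every factor named in the matching sentence.

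**Conclusion.** The point holds in conditional form. The matched-pair label does not fit a three-arm trial. The plan does not say what constrained allocation, and the Aim 1 models adjust for none of the matching factors. If the matching restricted allocation and still explains school differences after T1 and cohort adjustment, standard errors may be too wide and power may be lost.

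Under the assumptions above (ICC 0.05, d = 0.2, arm-only comparator), the effect of adding a set term runs from about 1 point of power lost at r = 0, through about 2 points gained at r = 0.1 and 9 at r = 0.3, to about 18 at the upper case of r = 0.5. The plan gives nothing that fixes r, so a definite loss cannot be claimed. The change is worth making because the contradiction needs correcting in any case, and the adjustment costs little even if the matching turns out to be uninformative.

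**What to change.** Replace the matched-pair label with the allocation actually used, and define the strata and blocks.

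- **If schools are randomised in matched sets** (for example triplets, one school per arm): keep the set identifier from the randomisation list. Add it as a random intercept to the Aim 1 T2 and longer-term models, with small-sample degrees of freedom, and fit it as a fixed effect in a sensitivity analysis.
- **If they are not:** delete the label and adjust the Aim 1 models for the factors used in matching or stratification, namely school size and performance together with the randomisation strata.

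The cost is a few sentences in section 6.1, section 4.4 and section 9, plus one or a few model terms built from information the trial should already hold. The statistical price is a few denominator degrees of freedom (at most about 11), or about 1 point of power if the matching is uninformative.
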